A separate analysis on efficacy and safety endpoints will be performed considering the extension phase duration, a period of an additional 6 months, lasting until the End of Extension Phase visit at Month 12.

As this is an extension phase following the main study phase, the efficacy and safety endpoints in the extension phase will be summarised descriptively. No formal statistical hypotheses testing will be performed.

Statistical analyses will include the following:

- For the continuous endpoints, the descriptive summary statistics (number of participants (n), mean, SD, median, minimum, maximum) will be calculated
- For the categorical endpoints, the summary statistics of number and percentage of participants and the exact two-sided 90% confidence interval (CI) will be calculated

The analysis sets for the efficacy endpoints will be the Intention-To-Treat set (ITT) and the per protocol (PP) set. Analyses and summary tables for the safety endpoints will be based upon the Safety population.

Sample size calculation: The number of participants included in the extension study will be dependent on the number of participants from study D-CN-52014-243 who give consent to continue into the extension study. A maximum of 32 participants will be expected to be enrolled in the extension phase.

PROTOCOL AMENDMENT SUMMARY OF CHANGES TABLE

DOCUMENT HISTORY	
Document	Date
Amendment 3	09 July 2021 (Version 4.0)
Amendment 2	16 March 2021 (Version 3.0)
Amendment 1	28 October 2020 (Version 2.0)
Original Protocol	27 July 2020 (Version 1.0)

The details of the previous amendments are provided in [Appendix 2](#).

Amendment 3 (09 July 2021, Version 4.0)

Overall Rationale for the Amendment:

This amendment includes minor updates and clarifications of study assessments, as well as alignment of common text with latest protocol template update.

Summary of change table from previous version of the protocol

Any new or amended text in the protocol is indicated in bold. Deletions are marked in strikeout text. Minor formatting and editing are not included.

Section	WAS (Version 3.0, 16 March 2021)	IS (Version 4.0, 09 July 2021)	Rationale
Title Page		Study Phase: III	Quality assurance requirement to follow latest protocol template update.
Title Page	
Emergency Contact: PPD
 
Ipsen Innovation ZI de [name] [name] [name] Mobile: PPD
		Aligned with current template

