		
serious.
 
Hospitalisation for elective treatment of a pre-existing condition that did not worsen from baseline is not considered an AE.
 
(4) Results in a persistent or significant disability/incapacity.
 
The term disability means a substantial disruption of a person's ability to conduct normal life functions. This definition is not intended to include experiences of relatively minor medical significance such as uncomplicated headache, nausea, vomiting, diarrhoea, influenza and accidental trauma (e.g sprained ankle) that may interfere with or prevent everyday life functions but do not constitute a substantial disruption.
	
11.4.4.1 / Primary Efficacy Endpoint	The GnRH stimulation test is performed by using i.v. injection of gonadorelin (synthetic GnRH) to stimulate gonadotrophin release, and blood samples will be collected prior to and 30, 60, 90 minutes after the gonadorelin injection for central assessment of serum LH levels.	The GnRH stimulation test is performed by using i.v. injection of gonadorelin (synthetic GnRH) to stimulate gonadotrophin release, and blood samples will be collected prior to and 30, 60, 90 minutes (± 5 minutes at each timepoint) after the gonadorelin injection for central assessment of serum LH levels.	More feasible to have a time window for blood collection
14.2 / Informed Consent for Participation in the Study	Prior to study entry, the Investigator, or a person designated by the Investigator, will explain the nature, purpose, benefits and risks of participation in the study to each participant, participant's legally acceptable representative or impartial witness. Written informed	
 The informed consent form and any participant/assent recruitment materials must be in compliance with ICH GCP, local regulatory requirements, and legal requirements, including applicable privacy laws. They must 	

Section	WAS (Version 3.0, 16 March 2021)	IS (Version 4.0, 09 July 2021)	Rationale

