- Any clinically significant abnormal laboratory findings or other abnormal safety assessments that are associated with the underlying disease, unless judged by the investigator to be more severe than expected for the participant's condition.
- The disease/disorder being studied or expected progression, signs or symptoms of the disease/disorder being studied, unless more severe than expected for the participant's condition.
- Medical or surgical procedure (e.g. endoscopy, appendectomy): the condition that leads to the procedure is the AE.

- Situations in which an untoward medical occurrence did not occur (social and/or convenience admission to a hospital).
- Anticipated day-to-day fluctuations of pre-existing disease(s) or condition(s) present or detected at the start of the study that do not worsen.

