8.1.5 Reporting of Serious Adverse Events

All SAEs (as defined below), regardless of treatment group or suspected relationship to triptorelin, must be reported immediately (within 24 hours of the Investigator's knowledge of the event) using the SAE report form via the email address or the fax number specified at the beginning of this protocol as well as recording them in the eCRF.

An SAE is defined as any untoward medical occurrence that, at any dose, meets one or more of the criteria listed:

- (1) Results in death

(2) Is life threatening. The term ‘life-threatening’ in the definition of ‘serious’ refers to an event in which the participant was at risk of death at the time of the event. It does not refer to an event, which hypothetically might have caused death, if it were more severe

(3) Requires in-patient hospitalisation or prolongation of existing hospitalisation.

In general, hospitalisation signifies that the participant has been admitted (usually involving at least an overnight stay) at the hospital or emergency ward for observation and/or treatment that would not have been appropriate in the physician’s office or outpatient setting. Complications that occur during hospitalisation are AEs. If a complication prolongs hospitalisation or fulfils any other serious criteria, the event is serious. When in doubt as to whether “hospitalisation” occurred or was necessary, the AE should be considered serious.

Hospitalisation for elective treatment of a pre-existing condition that did not worsen from baseline is not considered an AE

(4) Results in a persistent or significant disability/incapacity. The term disability means a substantial disruption of a person’s ability to conduct normal life functions.

This definition is not intended to include experiences of relatively minor medical significance such as uncomplicated headache, nausea, vomiting, diarrhoea, influenza and accidental trauma (e.g. sprained ankle) that may interfere with or prevent everyday life functions but do not constitute a substantial disruption.

(5) Results in congenital anomaly/birth defect in the offspring of a participant who received the triptorelin

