(6) Is an important medical event that may not result in death, be life threatening, or require hospitalisation but, based upon appropriate medical judgement, may jeopardise the participant and may require medical or surgical intervention to prevent one of the outcomes listed in this definition. Examples of such medical events include allergic bronchospasm requiring intensive treatment in an emergency room or at home, blood dyscrasias or convulsions that do not result in in-patient hospitalisation, or the development of drug dependency or drug abuse.

Medical or scientific judgment should be exercised by the Investigator in deciding whether SAE reporting is appropriate in other situations such as significant medical events that may jeopardise the participant or may require medical or surgical intervention to prevent one of the other outcomes listed in the above definition. These events should usually be considered serious.

Examples of such events include invasive or malignant cancers, intensive treatment for allergic bronchospasm, blood dyscrasias, convulsions or development of intervention dependency or intervention abuse.

A suspected or confirmed coronavirus COVID-19 (SARS-CoV-2) infection must be reported as serious (seriousness criteria should be “other medically significant” if no other seriousness criteria are present (e.g. hospitalisation).

- **Hospitalisation** is defined as any in-patient admission (even if less than 24 hours). For chronic or long-term in-patients, in-patient admission also includes transfer within the hospital to an acute/intensive care in-patient unit
- **Prolongation of hospitalisation** is defined as any extension of an in-patient hospitalisation beyond the stay anticipated/required for the reason for the initial admission, as determined by the Investigator or treating physician. For protocol-specified hospitalisation in clinical studies, prolongation is defined as any extension beyond the length of stay described in the protocol. Prolongation in the absence

of a precipitating, TEAEs (i.e. not associated with the development of a new AE or worsening of a pre-existing condition) may meet the criteria for "seriousness" but is not an adverse experience and thus is not subject to immediate reporting to the Sponsor

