- Preplanned or elective treatments/surgical procedures should be noted in the participant's screening documentation. Hospitalisation for a preplanned or elective treatment/surgical procedure should not be reported as an SAE unless there are complications or sequelae that meet the criteria for seriousness described above.

Any SAE must be reported immediately (within 24 hours), using the SAE report form via the email address or the fax number specified at the beginning of this protocol as well as recording them in the eCRF, independent of the circumstances or suspected cause, if it occurs or comes to the attention of the Investigator at any time during the study period.

Any AE/SAE with a suspected causal relationship to triptorelin administration occurring at any other time after completion of the study must be reported promptly, within 24 hours.

The following information is the minimum that must be provided to the Sponsor within 24 hours for each SAE:

- Study number
- Centre number
- Participant number
- AE
- Investigator's name and contact details.

The additional information included in the SAE form must be provided to the Sponsor or representative as soon as it is available. The Investigator should always provide an assessment of causality for each event reported to the Sponsor. Upon receipt of the initial report, the Sponsor will ask for the Investigator's causality assessment if it was not provided with the initial report.

The Investigator should report a diagnosis or a syndrome rather than individual signs or symptoms. The Investigator should also try to separate a primary AE considered the foremost untoward medical occurrence from secondary AEs that occurred as complications.

8.1.6 *Pregnancy*

Information regarding pregnancies must be collected as an SAE on the AE page of the eCRF and reported to the Sponsor within 24 hours as described in Section 8.1.5.

If pregnancy occurs during the study, the outcome of the pregnancy will be collected following completion of the study. The Sponsor will request further information from the Investigator as to the course and outcome of the pregnancy using the Standard Drug Exposure for Pregnancy Form.

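### Protocol Section 8.1.5 has two elective-admission rules of different scope, which conflict when a condition noted at screening worsens on study before a planned admission

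*Protocol*

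**What the plan says.** Both rules are current text in Protocol Section 8.1.5, Reporting of Serious Adverse Events.

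- Criterion (3) makes an untoward occurrence serious if it "Requires in-patient hospitalisation or prolongation of existing hospitalisation". Its explanatory text ends with an exemption: "Hospitalisation for elective treatment of a pre-existing condition that did not worsen from baseline is not considered an AE". Two conditions must both hold: the condition is pre-existing, and it has not worsened.
- After the numbered criteria, one bullet counts every in-patient admission as hospitalisation, however short, with no exception for elective stays.
- The last bullet of that list opens: "Preplanned or elective treatments/surgical procedures should be noted in the participant's screening documentation". It continues: "Hospitalisation for a preplanned or elective treatment/surgical procedure should not be reported as an SAE unless there are complications or sequelae", and adds that those complications or sequelae must meet the seriousness criteria. Neither condition from criterion (3) appears.

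Two parts of Section 8.1.1 also matter. Exacerbation of a pre-existing condition is an AE, and for a medical or surgical procedure "the condition that leads to the procedure is the AE".

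SAP Section 5.8.3 plans tables of SAEs, serious TEAEs and treatment-related serious TEAEs, plus a listing of all SAEs.

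**The concern.** A site has two instructions on one page for the same kind of admission, and only one asks whether the condition is pre-existing and unchanged. A site that follows the later bullet can withhold the serious label from an event that criterion (3) makes serious.

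The label has consequences here. Under Protocol Section 4.4, safety concerns are identified by reviewing SAEs as sites report them. There is no independent data monitoring committee (SAP Section 3.1) and there are no adverse events of special interest (Protocol Section 8.1.3). Expedited reporting under Protocol Section 8.1.9 starts from a serious classification, and the SAE outputs in SAP Section 5.8.3 contain only what was classified as serious.

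**Working it through.** The point rests on wording, so the check applies both rules to each type of elective admission.

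1. **Pre-existing condition, noted at screening, not worsened.** Criterion (3): not an AE. Bullet: not an SAE. No conflict.
2. **Any elective admission with a complication or sequela that meets a seriousness criterion.** Criterion (3): the complication is serious. Bullet: its own exception applies, so report. No conflict.
3. **Pre-existing condition, noted at screening, worsens on study, planned admission follows, no serious complication.** Section 8.1.1 makes the exacerbation an AE. The exemption in criterion (3) fails on its second condition, so the admission makes the AE serious and it is due within 24 hours. Bullet: do not report as an SAE. **Conflict.** The screening sentence does not help, because this procedure was noted at screening.
4. **New on-study condition, elective admission arranged later.** The exemption in criterion (3) fails on its first condition, so the event is an SAE. Bullet: exempt if its operative sentence is read alone, not covered if the opening sentence limits it to procedures known at screening. **Depends on the reading.**

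Could other text resolve case 3?

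- The tie-break in criterion (3), that "the AE should be considered serious", applies to doubt about whether hospitalisation occurred or was needed. It does not address elective status.
- The bullet's exception for complications or sequelae most naturally means consequences of the procedure or stay, not a worsening that came before it.

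This does not depend on the amendment history. The sentence in criterion (3) entered with Amendment 3, whose change table says "Any new or amended text in the protocol is indicated in bold". The later bullet is not in the table's 8.1.5 row, so it was probably carried over without alignment. That is an inference, because the Version 3.0 extract is abridged.

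Size: planned enrolment is 32 (Protocol Section 11.2). One event is 1/32 = 0.03125, or 3.1%. If case 3 occurs once and is the only SAE, the count is 1 under criterion (3) and 0 under the bullet. The documents give no figure for how often such admissions occur, so no expected number can be calculated.

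**The case against.** The best defence is that the rules work at two levels. The sentence in criterion (3) concerns AE status and the bullet concerns SAE reporting. An unchanged condition would then not be an AE at all, while other elective cases would be AEs that the admission alone does not make serious. On this view the bullet is a specific exception to a general criterion, and criterion (3) never says that its exemption is the only one. A site could add that worsening is itself a sequela, or that an admission fixed before the worsening was not required by it.

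Part of this stands: a direct contradiction is not the only possible reading. But the text does not set out the two levels, criterion (3) does not point to a further exception, and the hospitalisation definition has no elective carve-out. The exemption in criterion (3) also turns on worsening, which would have little purpose if a worsened condition were excused later in the section. Two careful sites can still classify case 3 differently.

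A reader might also infer more than the documents support:

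- *That the bullet exempts every elective admission.* It does not: complications and sequelae that meet a seriousness criterion stay reportable.
- *That a new on-study condition is plainly exempt.* The screening sentence supports a narrower reading, so this is the weaker case.
- *That the event disappears from the safety data.* It does not. Under Section 8.1.1 the underlying condition is still an AE, so it is recorded and assessed for causality, and it enters the TEAE tables if treatment-emergent. Criterion (6) and the paragraph on investigator judgement are separate routes to seriousness.
- *That one omitted event changes the safety conclusion.* The plan sets no SAE threshold or decision rule, and SAP Section 5.8.3 plans counts and percentages of AEs without confidence intervals. The supportable statement is that the reported SAE count could change.

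**Conclusion.** The concern holds in limited form. Section 8.1.5 has two elective-admission rules of different scope. They conflict for a condition noted at screening that worsens on study before a planned admission, and they are ambiguous for a new on-study condition. The effect is confined to events for which an elective admission is the only ground for seriousness. For those, the serious label, the 24-hour report and the entry in the SAE tables and listing are at risk. The treatment-related serious table is touched only if the event is judged related.

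Each event is worth 3.1 percentage points of SAE incidence if the denominator is the planned 32, and slightly more if the Safety population is smaller. This assumes that the bullet's exception does not cover a worsening that preceded admission. Efficacy analyses and sample size are unaffected. It is an inconsistency of wording worth correcting because it sits in the SAE reporting rule.

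**What to change.** Reconcile the bullet with criterion (3). Its exemption should apply only to a preplanned or elective procedure for a pre-existing condition that is noted in the screening documentation and has not worsened from baseline. Every other admission is assessed under criterion (3). Keep the existing exception for serious complications and sequelae.

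Use baseline as the single reference point and say once what it means here. Protocol Section 7.2 takes baseline values from the Screening visit, while SAP Section 5.1.3 takes the last measurement before the first injection. A worsening between the two would otherwise remain unclear.

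The cost is one sentence in Section 8.1.5 and a note to sites. The reported SAE count may rise slightly.

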Table 2	Schedule of Assessments in Extension Phase	44
Table 3	Composition of Triptorelin Pamoate 3-Month Formulation	48
Table 4	Composition of the Solvent for Suspension.....	48
Table 5	Secondary Efficacy Endpoints and Evaluations.....	50
Table 6	Efficacy Endpoints and Evaluations in the Extension Phase	51

LIST OF FIGURES

Figure 1 Main Study Design.....	34
Figure 2 Extension Phase Design	34

LIST OF ABBREVIATIONS

ABBREVIATION	Wording Definition
AE(s)	Adverse Event(s)
ALP	Alkaline Phosphatase
ALT	Alanine Aminotransferase
AST	Aspartate Transaminase
BA	Bone Age
BMI	Body Mass Index
CA	Chronological Age
CBC	Complete Blood Count
CE	Conformité Européenne
CRF	Code of Federal Regulations (US)
CI	Confidence Interval
CPP	Central Precocious Puberty
CRO	Contract Research Organisation
CSR	Clinical Study Report
EC	Ethics Committee
eCRF	Electronic Case Report Form
EDC	Electronic Data Capture
EOS	End of Study
FSH	Follicle-stimulating Hormone
GCP	Good Clinical Practice
GLP	Good Laboratory Practice
GMP	Good Manufacturing Practice
GnRH	Gonadotropin-releasing Hormone
GnRHa(s)	GnRH Agonist(s)
IB	Investigator's Brochure
ICH	International Council for Harmonisation of Technical Requirements for Pharmaceuticals for Human Use
IEC	Independent Ethics Committee
IGF-1	Insulin-like Growth Factor 1
i.m.	Intramuscular
INN	International Non-proprietary Name
IRB	Institutional Review Board
ITT	Intention-to-treat

ABBREVIATION	Wording Definition
IU	International Units
i.v.	Intravenous
IWRS	Interactive Web Response System
LH	Luteinising hormone
LHRH	Luteinising Hormone-releasing Hormone
MAH	Marketing Authorisation Holder
MDSS	Material Data Safety Sheets
MedDRA	Medical Dictionary for Regulatory Activities
miITT	Modified intention-to-treat
N	Number of Participants
NCI-CTCAE	National Cancer Institute – Common Terminology Criteria for Adverse Events
PASS	Power Analysis and Sample Size
PIL	Patient Information Leaflet
PK	Pharmacokinetic
PP	Per Protocol
PR	Prolonged Release
PT	Preferred Term
SAE	Serious Adverse Event
SAP	Statistical Analysis Plan
SAS®	Statistical Analysis System®
SD(s)	Standard Deviation(s)
SMP	Safety Management Plan
SOC	System Organ Class
SOP	Standard Operating Procedure
SUSAR(s)	Suspected Unexpected Serious Adverse Reaction(s)
t½	Plasma Half-life
TEAE(s)	Treatment-emergent Adverse Event(s)
ULN	Upper Limit of Normal
WHO-DD	World Health Organization Drug Dictionary

1 BACKGROUND INFORMATION

1.1 Introduction

Precocious puberty is a condition that causes early sexual development in girls and boys. While the chronological age (CA) limit for the onset of puberty is 8 years in girls and 9 years in boys for children in North America and Western European countries [Carel 2008], children with precocious puberty exhibit precocious pubertal development that can be 2.5 to 3 standard deviations (SDs) earlier than the current estimated average. The prevalence of precocious puberty is 10 times higher in girls than in boys [Carel 2008].

In a minority of children, precocious puberty can occur due to an organic lesion (cerebral tumour); in most children, this condition is caused by the early release of gonadotropin-releasing hormone (GnRH, also known as luteinising hormone-releasing hormone; LHRH) by the hypothalamus. In healthy children, GnRH stimulates the release of pituitary gonadotropins follicle-stimulating hormone (FSH) and luteinising hormone (LH), which is then followed by prolonged suppression of these hormones, contributing to normal pubertal development. The form of precocious puberty caused by early GnRH stimulation is termed central precocious puberty (CPP). In children with CPP, early GnRH release leads to the precocious secretion of LH and FSH which, in turn, activate the early secretion of gonadal hormones by the ovaries or testes.

Signs of puberty include pubic and axillary hair growth and changes in the child's body shape and behaviour. Boys develop facial hair and their penis lengthens and girls develop breasts and may have menstrual periods. In children with CPP, these signs prematurely appear before the age of 8 and 9 in girls and boys, respectively. Furthermore, growth velocity accelerates, initially inducing a rapid height increase, which stops at an early age. Accelerated bone maturation leads to premature epiphyseal closure and a final height below the target height that was otherwise expected for the child's age. These premature changes may also lead to psychological disorders in children with CPP.

There is currently no nationwide epidemiology study of CPP data in China. Only two studies have been published about the incidence of precocious puberty in two cities: Jiu Jiang (study with 3,312 children investigated and an incidence of 0.68%, 1.25% in girls and 0.11% in boys) [Hu 2012] and Zhengzhou (study with 8,750 children investigated and an incidence of 0.74%, 1.37% in girls and 0.26% in boys) [Wei 2010]. In coastal areas of China, precocious puberty has an incidence rate of 0.38%; the incidence in girls is higher at 0.67%. The prevalence of precocious puberty in Shanghai is 100/10,000 [Lin 2004]. These data refer to precocious puberty without GnRH-dependent stimulation, which is not specific for CPP and are probably lower than numbers described above.

As reported by Carel and Léger [Carel 2008], the assessment of gonadotropin levels (based on ultrasensitive assays) is central to the diagnosis of CPP. The gold standard for evaluation is the measurement of gonadotropin levels after stimulation with GnRH or a GnRH agonist (GnRHa). Peak LH levels of 5 to 8 IU/L suggest progressive CPP but there is an overlap between prepubertal and early pubertal values [Carel 2008, Resende 2007]. Caution should be taken when interpreting gonadotropin levels in children younger than 2 to 3 years old as gonadotropin levels are normally high in this age group [Carel 2008].

In CPP (i.e. with no other identified cause such as a cerebral tumour), there is no surgical therapy available and no effective alternative therapeutic option other than taking a prolonged release (PR) formulation of synthetic GnRH. In severe cases, untreated CPP causes physical and psychological problems for the child.

Treatment with GnRH analogues, which act by downregulating pituitary GnRH receptors [Carel 2009, Comite 1981 Crowley 1981, Bertelloni 2013], represent the standard of care for

the treatment of CPP [\[Carel 2009\]](#). Their efficacy to stop precocious development has been demonstrated and their use involves only minor adverse events (AEs). A review of CPP treatment by Krishna et al confirmed that treatment with PR formulations of GnRHs is safe, with relatively minor side effects, and supported that the outcome in terms of final height is favourable in most patients [\[Krishna 2019\]](#).

Diphereline® (international non-proprietary name (INN): triptorelin) is a synthetic GnRH analogue that is mainly characterised by the replacement of the L-glycine in the 6th position by a D-tryptophan. This structural modification increases both the resistance to enzymatic degradation and the affinity to the pituitary receptor, thus prolonging the plasma half-life ($t_{1/2}$) and increasing the potency of the drug.

In China, Diphereline® is available as a 1-month formulation, which is approved for use in patients with prostate cancer, CPP, endometriosis, fibromyomas and female infertility, and a 3-month formulation (containing 15 mg of triptorelin pamoate to ensure the release of 11.25 mg of product), which is approved for prostate cancer.

Several studies have assessed the efficacy and safety of triptorelin 3-month PR release formulation, including three Ipsen-sponsored phase III studies and two independent studies [\[Carel 2006, Martinez-Aguayo 2006, Zenaty 2016\]](#). In 2017, Durand et al. [\[Durand 2017\]](#) performed a meta-analysis to assess the data available from a total of 153 children with CPP (13 boys and 140 girls) that had participated in the clinical studies and received treatment with this triptorelin formulation. Across all studies, the primary outcome was the proportion of children with suppressed LH response (peak LH ≤ 3 IU/L) to the GnRH test 3 months after triptorelin injection. Secondary outcomes included the proportion of children with suppressed peak LH response at 6 months, and the proportion of children with suppressed peak FSH response (≤ 3 IU/L), proportion of girls with suppressed oestradiol (≤ 20 pmol/L) and proportion of boys with suppressed testosterone (≤ 30 ng/dL) at 3 months [\[Durand 2017\]](#). The authors concluded that the 3-month formulation of triptorelin was efficacious in suppressing LH peak and other gonadal hormones and in slowing the progression of CPP in children.

The worldwide marketing status of all triptorelin formulations of which Ipsen is the marketing authorisation holder (MAH) can be found in the Investigator's Brochure (IB). Further details/additional information regarding risks and benefits to participants may also be found in the IB.

A more detailed description of the product is provided in Section 3.7 and Section 6. Further details on administration procedures and dosage are provided in Section 6.2.

